6.5.3 General Exclusion Criteria

Subjects must not meet any of the following exclusion criteria:

- 1. Requires urgent or emergent TAVR procedure
- 2. Contraindicated to MRI
- 3. Previously implanted aortic or mitral valve bioprosthesis
- 4. Hepatic failure (Child-Pugh class C)
- 5. Hypercoagulable state that cannot be corrected by additional periprocedural heparin
- 6. Planned to undergo any other cardiac surgical or interventional procedure (e.g., concurrent coronary revascularization) during the TAVR procedure or within 30 days prior to the TAVR procedure. NOTE: Diagnostic cardiac catheterization is permitted up until baseline MRI is obtained. Once baseline MRI is obtained, no additional intra-aortic or intracardiac procedure may occur.
- 7. Acute myocardial infarction within 30 days of the planned index procedure
- 8. Renal failure, defined as estimated glomerular filtration rate (eGFR) <30 mL/min
- 9. Documented history of stroke or TIA within the prior 6 months, or any prior stroke with a permanent major disability or deficit (NIHSS >1 at baseline)
- 10. Left ventricular ejection fraction ≤30% within 3 months prior to procedure
- 11. History of intolerance, allergic reaction, or contraindication to any of the study medications, including heparin, aspirin, clopidogrel, or a sensitivity to contrast media or anesthesia that cannot be adequately pre-treated
- 12. Known allergy or sensitivity to nickel-titanium
- 13. Active endocarditis or ongoing systemic infection, defined as fever (>38°C) and/or white blood cell (WBC) >15,000 IU

- 14. Undergoing therapeutic thrombolysis
- 15. History of bleeding diathesis or a coagulopathy
- 16. Known or suspected to be pregnant, or is lactating; female subjects of child-bearing potential must have a negative serum or urine pregnancy test within 48 hours prior to the index study procedure.
- 17. Currently participating in another drug or device clinical study
- 18. Any other clinical reason, as deemed by the investigators of the study, by which the patient would not be an appropriate candidate for the study
- 19. Vulnerable subject populations (e.g., incarcerated or cognitively challenged adults)

7.0 STUDY METHODOLOGY

Study assessments and data collection points are visually represented in **Figure 6** and **Table 2** and are described below. To avoid missing data in the study, subjects should be followed for all regularly scheduled visits for safety and effectiveness assessments. Any reason for withdrawal from the study should be documented as described later in the protocol. See **Section 13.0** for definitions of endpoint-related terms used in this section.

Study procedures should be followed carefully as they have been designed to address any known or foreseeable factors that may compromise the outcome of the clinical study or the interpretation of results (e.g., subject baseline characteristics, concomitant medication, the use of other medical devices, and subject-related factors such as age, gender, or lifestyle) and methods for addressing these factors (e.g., subject selection, statistical analysis).

Figure 6: Study Flow Diagram

	Screening /		Follow-Up	
	Baseline (within 14 days of procedure, unless specified)	Treatment Procedure	Pre-Discharge ¹	30 Days (+/- 7 days)
Visit type ►	Clinic	Clinic	Clinic	Clinic
Subject informed consent	Х			
Demographics & medical history	Х			
Ejection fraction ²	Х			
Inclusion/exclusion criteria	Х			
Pregnancy test (serum/urine) ³	Х			
National Institute of Health Stroke Scale (NIHSS)	Х		Х	
Montreal cognitive assessment	Х			Х
Modified Rankin Scale	Х			Х
Computed Tomography (CT)	X ⁴			
MRI (assessed by independent reader)	X ⁵		X ₆	
Medication assessment (anticoagulants and antiplatelet agents only)	Х	Х	Х	Х
Labs (GFR, troponin, CBC)	Х		X ⁷	X ⁸
Device performance assessment		Х		
Gross & histological assessment of debris captured by the EmStop (assessed by core lab)		х		
Adverse event assessment		Х	X	X

Table 2: Schedule of Study Activities

¹Assessments occur prior to discharge or 7 days post-op, whichever occurs first.

²Will be obtained as standard of care within 3 months of procedure. If not in medical history, must be obtained prior to TAVR procedure per exclusion criteria.

³If female with child-bearing potential.

⁴CT is performed during TAVR screening; the images will be reviewed to confirm that angiographic eligibility criteria are met.

⁵MRI (DWI and T2-FLAIR) is conducted within 14 days pre-procedure and will be assessed by an independent reader.

⁶MRI (DWI and T2-FLAIR) is conducted 18-36 hours post-procedure and will be assessed by an independent reader.

⁷Pre-discharge labs will be collected within 72 hours post-procedure. CBC to include RBC, hemoglobin, hematocrit, WBC, and platelets. ⁸Only lab collected at 30 days is GFR.

7.1 Screening Visit

The study team will screen patients for the study. Screening is defined as the process of reviewing a patient's medical records against the study eligibility criteria to determine if the patient is eligible to enroll in the study. It is expected that the medical records will contain adequate information to determine if a patient meets most of these criteria; this includes the computed tomography (CT) completed as part of the standard of care TAVR screening process. The investigator will visually assess the CT imaging to ensure angiographic inclusion criteria are met.

If the investigator (or designee) determines the patient meets all clinical inclusion and exclusion criteria (except criteria verified by blood or urine testing after consent), they can be consented for study participation, after which all remaining non-angiographic eligibility criteria will be verified prior to the procedure.

Sites will be required to maintain a screen failure log that contains rationale for subjects who became screen failures after consent.

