3.3 Proposed Indications for Use

The EmStop Embolic Protection System is indicated for use as an embolic protection device to capture and remove thrombus/debris while performing transcatheter aortic valve replacement procedures. The diameters of the aorta at the site of filter placement should be between 25 – 40mm.

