6.5.2 Angiographic Inclusion Criteria (assessed via computed tomography)

- 5. Subject anatomy is compatible with correct device deployment and positioning with:
 - Ability to achieve access with a 21 French equivalent femoral access sheath
 - Ascending aorta length ≥8 cm
 - Ascending aorta/aortic arch diameter is ≥ 25 or ≤40 mm
 - Ascending aorta or aortic arch exhibits ≤ Grade 1 atheromatous disease and limited wall calcification

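### The anatomical entry limits are numeric and device-dependent, but the protocol neither requires them to be measured on the CT nor provides for recording the values

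*Combined protocol and SAP*

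**What the plan says.** Section 6.5.2 lists the anatomy required for correct deployment, to be judged on CT. Three items are numeric: "Ascending aorta length ≥8 cm", "Ascending aorta/aortic arch diameter is ≥ 25 or ≤40 mm" and "Ability to achieve access with a 21 French equivalent femoral access sheath". The fourth, atheroma grade and limited wall calcification, is a graded judgement. The synopsis words the diameter item in the same way.

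The limits follow the device. Table 1 gives an aorta compatibility of 25 to 40 mm and a 21F introducer sheath. Section 3.3 states "The diameters of the aorta at the site of filter placement should be between 25" to 40 mm.

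On verification, section 7.1 says "The investigator will visually assess the CT imaging to ensure angiographic inclusion criteria are met". Footnote 4 to Table 2 says "the images will be reviewed to confirm that angiographic eligibility criteria are met". The CT is the routine pre-TAVR scan held in the medical records ("this includes the computed tomography (CT) completed as part of the standard of care TAVR screening process").

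Section 7.4 lists what is documented on eCRFs at baseline: history, pregnancy test, ejection fraction, medication, laboratory values, MRI and three scales. No aortic or femoral dimension appears there. The analysis sections (8.3 to 8.7) plan descriptive summaries and one subgroup analysis, for operator learning.

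**The concern.** A limit in centimetres, millimetres or French size can be applied consistently only if someone measures, at a stated level. The protocol states neither the act nor the level. The level matters here: the entry criterion names the ascending aorta and arch, while the indication refers to the place where the filter sits.

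The primary performance endpoint, device procedural success, depends on getting the system in, deployed, positioned and out again without interfering with the TAVR system. Section 6.5.2 itself presents the anatomical limits as the conditions for correct deployment and positioning. Sections 6.1 and 8.8 say the results are to inform the design of later studies. If a device fails in one of 15 subjects, the first question is whether the anatomy was inside the intended range, near its edge or outside it. The protocol does not require the value that would answer this to be collected before the outcome is known.

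**Working it through.** The plan has no figure of its own to reproduce here; N = 15 is not derived from power (section 8.8). The check is mainly a comparison of sections, with some arithmetic for scale.

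**1. Is a measurement required or recorded anywhere?**
- Section 6.5.2: numeric limits, judged on CT; no method, plane or level.
- Section 7.1: visual assessment by the investigator. After consent, only the criteria that are not angiographic remain to be verified.
- Table 2: a CT row at screening/baseline, with a footnote on image review and no dimension to be recorded.
- Section 7.4: no CT value on the eCRF list.
- Section 9.0: independent assessment for pathology and MRI, none for CT.
- Section 12.6: the minimum for full source verification names consent, endpoint and adverse event data; eligibility is not named.

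No section requires a dimension to be measured or entered.

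**2. The diameter criterion as written.** Let d be the diameter. If d is 25 mm or more, the first condition holds. If d is below 25 mm, it is also at or below 40 mm, so the second holds. Every diameter therefore passes, which conflicts with the closed 25 to 40 mm range in Table 1 and section 3.3.

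**3. Weight of one subject.** 1/15 = 6.7%. Clopper-Pearson 95% intervals:
- 15/15: lower limit 0.025^(1/15) = 78.2%, upper limit 100%.
- 14/15: lower limit is the 2.5% quantile of Beta(14, 2) = 68.1%; upper limit 0.975^(1/15) = 99.8%.

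A single failure moves the lower limit by 78.2 − 68.1 = 10.1 percentage points.

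**4. Illustration of misreading at the 40 mm limit.** Assumption: unbiased normal reading error with SD s, a figure the documents do not give. P(read as 40 mm or less) = Φ((40 − true diameter)/s).

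| True diameter | s = 1 mm | s = 2 mm | s = 3 mm |
|---|---|---|---|
| 41 mm | 16% | 31% | 37% |
| 42 mm | 2% | 16% | 25% |

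These are conditional on an aorta truly at 41 or 42 mm. They are not a rate of ineligible enrolment, because the documents do not say how often such patients present.

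**5. Could an association be tested?** Suppose diameters were recorded, with 5 near-limit and 10 other subjects (assumed split). A two-sided Fisher test at 0.05 has about 22% power for success of 60% versus 95%, and about 52% for 40% versus 95% (assumed rates). A test would tell little; a listing needs no power.

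**The case against.** The strongest reply is that assessing a CT visually does not exclude measuring on it. The limits are to be judged on CT and the investigator must ensure that they are met, which for a length in centimetres is compatible with using callipers. Image review also suits the atheroma and calcification items. This stands: the wording leaves unmeasured entry possible but does not show that it would happen.

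A reader might go further and infer that a monitor could not verify eligibility, that no record of anatomy would exist, or that fit could never be related to performance. The documents do not support this. Section 12.1.3 requires investigators to keep diagnostic test results and data on each subject's condition at entry. Section 12.6 has monitors check against source and hospital charts, and its list of fully verified items is only a minimum. Section 12.12 gives direct access to source. The scans can be measured during or after the study.

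Nor does absence from section 7.4 prove that no CT field exists. That section describes the baseline visit, Table 2 has its own CT and eligibility rows, and the eCRFs, the Monitoring Plan and the separate SAP named in section 8.9 are not in the document reviewed. What remains is that the protocol does not itself call for the values. Measurement done afterwards would follow knowledge of outcome and would lack a prespecified method.

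It is also fair to say that anatomy-by-outcome analysis is no part of a descriptive study of 15. That tells against a test, not against a per-subject listing.

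**Conclusion.** The point holds as a gap in what the protocol requires. Entry against device-dependent numeric limits is not tied to a measurement, and the values needed to interpret a failure, debris count or infarct burden are not called for. It is a cheap improvement that should be made; it does not undermine the design, the sample size or the planned summaries.

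The effect on enrolment cannot be sized from the documents. The 16 to 37% (41 mm) and 2 to 25% (42 mm) misreading probabilities rest on an assumed error SD of 1 to 3 mm and apply only to truly borderline aortas. The firmer quantity is that each subject carries 6.7% of the primary performance result.

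The literal reading of the diameter criterion needs no assumption: as written it excludes no one and is inconsistent with Table 1 and section 3.3. Which wording is intended is for the sponsor to settle.

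**What to change.** - **Section 7.1 and Table 2, footnote 4:** state that ascending aorta length, aortic diameter (at the planned filter site and in the arch) and femoral access diameter are measured on the existing TAVR-planning CT, and how. Leave atheroma grade and calcification to image review.
- **Section 7.4:** add these items to the baseline eCRF: length, the two aortic diameters, access diameter, atheroma grade and calcification, about six fields.
- **Section 12.6:** include them in the data verified against source.
- **Section 8 or the SAP:** give a descriptive per-subject listing of these values beside device procedural success, debris count and infarct burden, with no association test.
- **Section 6.5.2 and the synopsis:** reconcile the diameter criterion with Table 1 and section 3.3.

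The cost is a few minutes per subject on a scan already acquired, plus the eCRF fields. No new imaging, additional reader or change in N is needed.

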7.2 Informed Consent Process

Prior to enrolling subjects in this study, the site will be required to have an Institutional Review Board (IRB) approved informed consent form (ICF). To ensure compliance with informed consent requirements, the sponsor or contract research organization (CRO) must review any modifications made to the sponsor's template ICF prior to IRB submission.

Written informed consent will be obtained from the patient (or the patient's legal representative, if applicable) prior to participation as a subject in the study. The investigator (or authorized designee) will explain the nature of the planned treatment and objectives of the study to the patient, along with any costs to the subject, payments for participation, and types of insurance provided (if applicable). The investigator will allow adequate time for the patient to read and review the consent form and to ask questions. When the investigator has reasonable assurance that the patient (or legal representative) has an acceptable level of comprehension and the patient (or legal representative) voluntary agrees to participate, the patient (or legal representative) and the investigator (or authorized designee) will sign and date the ICF.

The site will retain the original signed ICF in the subject's study records and will provide a copy of the signed ICF to the subject. The site will document the consent process (e.g., that the subject was consented, the date on which the consent was obtained, and that a copy of the signed ICF was given to the subject) in the subject's medical records.

Subjects will be informed of any new information that may make him/her change their mind about staying in the study. Subjects may be asked to sign a new ICF if this occurs.

7.2.1 Vulnerable Population

To preserve the ethical integrity of this study, the sponsor does not intend to enroll vulnerable subject populations (e.g., incarcerated persons or adults with severe cognitive challenges) in

this study since such populations may be coerced or compelled to participate in a clinical study without a full understanding or against their will these subjects should be excluded (in consideration of ISO 14155:2020 sections 5.7 and A.6.3).

7.3 Point of Enrollment & Numbering of Study Subjects

A patient will be considered enrolled as a study subject once an investigational EmStop System has entered the subject. The lowest available subject number will be assigned, progressing sequentially for each enrolled subject thereafter. The CRO will be notified of subject enrollment via the electronic data capture (EDC) database.

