3.0 TREATMENT DESCRIPTION

3.1 Device Description

The EmStop Embolic Protection System (EmStop System) is a catheter-based filter system that captures and removes debris dislodged during transcatheter aortic valve replacement (TAVR) procedures. The EmStop System is composed of a preloaded introducer sheath, delivery catheter, and filter sheath (**Figure 1**), as described below. Refer to **Table 1** for system specifications.

• Figure 1: EmStop Embolic Protection System

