3.1.1 Introducer sheath

The introducer sheath is a single lumen, braid-reinforced catheter used to gain access to the vasculature and to facilitate placement and removal of the filter sheath and delivery catheter (**Figure 2**). The proximal end of the introducer sheath comprises a hub with Tuohy Borst cap and a one-way stopcock for flushing.

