5.0 ENDPOINTS

5.1 Primary Safety Endpoint

The primary safety endpoint for the study is the occurrence of MACCE at 30 days, defined as a composite of the following VARC-2 defined components:

- All-cause mortality
- All stroke (disabling and non-disabling)
- Acute kidney injury (AKI) Stage 2 or 3 (including renal replacement therapy) within 72 hours

5.2 **Primary Performance Endpoint**

The primary performance endpoint for the study is device procedural success, defined as successful insertion, deployment, positioning, and removal of the EmStop System in the absence of device interference.

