7.5 Treatment Visit

The EmStop System will be prepared and flushed per the device Instructions for Use (IFU). A guidewire will be advanced to the ascending aorta, and the EmStop System will be loaded onto the proximal end of the guidewire for delivery and deployment within the ascending aorta. A commercially available Abbott or Medtronic transcatheter heart valve delivery catheter will be inserted through the EmStop System filter sheath, and the TAVR procedure will proceed according to standard of care. After the TAVR delivery catheter is removed, the EmStop filter will be collapsed into the in-line sheath and the EmStop System will be removed.

The assessments described below will be performed and results will be recorded on the relevant eCRFs.

- Adverse event assessment
- Device performance assessment
- Medication assessment (anticoagulants and antiplatelet agents only)
- Debris captured by the EmStop System filter will be sent for gross and histological assessment following the Pathology Core Lab Guidelines

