8.0 STATISTICAL METHODS

8.1 Analysis Data Sets

The primary analysis will consist of all available data on all subjects enrolled, referred to in ICH E9 ("Statistical Principles for Clinical Trials") as the full analysis set. As the study is a treatmentonly, single arm design, summaries of results will principally be presented for the entire study population.

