12.3 Device Accountability

All EmStop System investigational devices will be labeled with reference (part or model) and lot numbers. Shipment and receipt records will be maintained, and upon receipt of the investigational devices, the site study coordinator (or delegate) will inventory the devices. As each subject receives treatment with the study device, the date of treatment, subject identifiers (site number/subject number), device performance assessment, and device traceability information will be recorded. If a study device is returned to the sponsor, the date of return and reason for the return shall be documented.

The EmStop System must be stored in a secure location at each clinical site to ensure use only in the study and unused devices must be returned promptly upon study completion or termination. Product labeled as "For Investigational Use Only" must only be used in the clinical investigation.

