13.2 Other Study-Specific Definitions

Device interference: Interaction of the EmStop System with the TAVR system that leads to:

- Inability to advance or manipulate the TAVR system, or
- Inability to deploy the TAVR system, or
- Inability to retrieve the TAVR system

Device procedural success: Successful insertion, deployment, positioning, and removal of the EmStop System in the absence of device interference.

Major adverse cardiac and cerebrovascular events (MACCE): All-cause mortality, all stroke (disabling and non-disabling) and transient ischemic attack (TIA), and acute kidney injury (AKI) Stage 2 or 3 (including renal replacement therapy). MACCE events will be adjudicated by the Medical Monitor using VARC-2 definitions [*Kappetein 2013*].

Montreal cognitive assessment (MoCA): A highly sensitive tool for early detection of mild cognitive impairment that was validated in 2000. [https://www.mocatest.org/]

National Institutes of Health Stroke Scale (NIHSS): A systematic assessment tool that provides a quantitative measure of stroke-related neurologic deficit. [https://www.nihstrokescale.org/]

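### Device procedural success is computed only over patients the device has entered, so an attempt abandoned with nothing across the access site is left out of the rate

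*Combined protocol and SAP*

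**What the plan says.** Enrollment (Section 7.3): "A patient will be considered enrolled as a study subject once an investigational EmStop System has entered the subject". Subject numbers are given to enrolled subjects in sequence.

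Analysis set (Section 8.1): "The primary analysis will consist of all available data on all subjects enrolled". Section 8.4 summarises the performance endpoint descriptively and names no other set.

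Endpoint (Section 5.2): device procedural success is "defined as successful insertion, deployment, positioning, and removal of the EmStop System in the absence of device interference". Section 13.2 repeats this definition. It defines device interference but neither insertion nor entry.

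Device (Section 3.1): "The EmStop System is composed of a preloaded introducer sheath, delivery catheter, and filter sheath". Section 3.1.1 describes the introducer sheath as "used to gain access to the vasculature and to facilitate placement and removal of the filter sheath and delivery catheter".

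Procedure (Section 7.5): once a guidewire is in place, "the EmStop System will be loaded onto the proximal end of the guidewire for delivery and deployment within the ascending aorta".

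Purpose (Section 8.8): 15 subjects, chosen to inform a later pivotal study, with no power calculation and no success criterion.

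**The concern.** A patient must pass through entry to join the denominator, while insertion is one of the outcomes that the numerator measures. The denominator therefore depends on part of the outcome. If introduction is begun and EmStop is then abandoned with nothing across the access site, insertion has failed in the plainest sense, but the patient is never enrolled and cannot count as a failure.

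The omission can only favour the device. Because the study is descriptive and tests no hypothesis on this endpoint, the reported proportion is itself the product, and it is meant to feed the design of the pivotal study. A reader who takes it as success per attempted use could be misled by one or two cases, since each case weighs heavily at this sample size.

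**Working it through.** **Tracing the rule.** The plan gives no target or expected success rate, so there is no stated figure to reproduce. Three situations follow from Sections 7.3, 8.1 and 13.2:

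| Situation | Enrolled (7.3)? | In the rate (8.1)? |
|---|---|---|
| A component enters, then advancement, deployment, positioning or removal fails | Yes, on the natural reading | Yes, as a failure |
| First unit does not enter, a replacement unit does | Yes: 7.3 asks for an EmStop System, not the first one opened | Yes |
| Introduction begun, EmStop abandoned, no component across the access site | No | No |

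Only the third row is lost. The first row relies on the introducer sheath being part of the system (Sections 3.1 and 3.1.1), because entry is not defined.

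**Effect of a given number of cases.** Let s be the successes among 15 enrolled (Section 6.2 caps enrollment at 15) and f the number of abandoned non-entries. The reported rate is s/15 and the rate by attempt is s/(15+f). The 95% intervals are Clopper-Pearson, added here; Section 8.2 specifies only counts and percentages.

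| f (assumed) | s = 15 | s = 14 |
|---|---|---|
| 0 (as reported) | 15/15 = 100% (78.2 to 100) | 14/15 = 93.3% (68.1 to 99.8) |
| 1 | 15/16 = 93.8% (69.8 to 99.8) | 14/16 = 87.5% (61.7 to 98.4) |
| 2 | 15/17 = 88.2% (63.6 to 98.5) | 14/17 = 82.4% (56.6 to 96.2) |

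One case moves the rate by 100 − 93.75 = 6.25 points when s = 15, and by 93.3 − 87.5 = 5.8 points when s = 14. If the lost patient is not replaced, the report is 14/14 (100%, 76.8 to 100) against 14/15 (93.3%, 68.1 to 99.8).

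**Expected effect.** Let q be the chance of abandoned non-entry per attempt and p the success rate among entered cases. Success by attempt is p(1 − q), so the overstatement is p − p(1 − q) = pq for a fixed number of attempts, and at most that if enrollment continues to 15. The documents do not give q; the values below are assumptions for scale only. At q = 0 there is no bias.

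| q (assumed) | Chance of at least one case before 15 enrolled, 1 − (1 − q)^15 | Expected overstatement, p = 1, enrolling to 15 | Bound pq at p = 0.9 |
|---|---|---|---|
| 1% | 14% | 0.9 points | 0.9 points |
| 2% | 26% | 1.9 points | 1.8 points |
| 5% | 54% | 4.7 points | 4.5 points |
| 10% | 79% | 9.4 points | 9.0 points |

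Even a perfect 15/15 has a lower limit of 78.2%, about 22 points below the estimate. At low q the bias is small beside that uncertainty.

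**The case against.** The strongest reply is that the event is rare and nothing turns on it. Femoral access is obtained and the guidewire is at its target before EmStop is loaded (Section 3.2), and 21F access is an eligibility criterion judged on CT (Sections 6.5.2 and 7.1). The study is descriptive, and success among patients the device entered is a legitimate quantity to report. A non-entry would probably leave a trace in the post-consent screen failure log (7.1), in device deficiency collection (11.2.1) or in the record of returned devices (12.3). With at most 2 sites and 15 subjects, the sponsor would probably know of it.

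Most of this stands and it limits the weight of the point. It does not close the gap: none of those records is said to feed the success rate, and a rate that names insertion as a component yet excludes complete failure to enter needs a companion figure.

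A reader might infer more than the text supports:

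- *That insertion failures in general are lost.* On the natural reading, failures after any component enters are counted, as is a patient in whom a replacement unit enters.
- *That the learning-curve split in Section 8.7 mislabels the first case.* That section speaks only of subjects, a word that 7.1 also uses for screen failures. A non-entry gives little experience of deploying or retrieving the device, so calling the next patient first is defensible.
- *That Section 12.3 confines performance data to enrolled subjects.* Its wording, "As each subject receives treatment with the study device, the date of treatment, subject identifiers (site number/subject number), device performance assessment", concerns device accountability. Section 7.5 and Table 2 place the performance assessment at the procedure without an enrollment condition.
- *That the bias is large.* The 5% and 10% rows are assumptions with no support in the documents.
- *That the whole plan lacks an attempted-use set.* Section 8.9 defers analytical detail to a separate SAP that is not in the available text.

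**Conclusion.** The point holds in a narrow form and is minor. As written, Sections 7.3 and 8.1 leave one kind of insertion failure, abandonment with no component across the access site, out of an endpoint that includes successful insertion. The direction is certain: any bias is upward. Its size is not known. One case is worth about 6 points at this sample size, and the expected overstatement is at most pq, which is zero if non-entry never occurs.

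The conclusion assumes that entry of any component counts as entry and that the unseen SAP does not already define a set for attempts. No decision in this study depends on the rate. The consequence is for how the figure is read when the pivotal study is planned.

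**What to change.** - Keep the enrollment point in Section 7.3 and the enrolled set for MACCE.
- In Sections 8.1 and 8.4, also report device procedural success for all consented patients in whom introduction of any EmStop component at the access site is begun. Count abandoned non-entry as failure and show the entered-only rate beside it.
- In Section 7.3 or 13.2, state that entry of any component, including the introducer sheath, counts as entry.
- List each non-entry case with the attending physician and its place in that physician's case order. It is then visible beside the Section 8.7 split without redefining which subject is first.
- If the separate SAP already contains such a set, a cross-reference from Section 8.4 would serve in place of the second change.

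The cost is some protocol wording, one small listing and possibly a slightly lower success rate. No enrollment place is used and the sample size does not change.
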